## Background

Motor impairment is a hallmark feature of Parkinson's disease (PD). The motor-based symptoms are characterized by reduced amplitude and speed of movement and difficulty initiating and coordinating movement. An important functional consequence of these motor-based impairments is a marked reduction in speaking intensity. This condition, known as hypophonia, is estimated to effect approximately 75% of patients in some stage of the disease process.

Our two current, evidence-based treatments for hypophonia, LSVT LOUD® and the SpeechViveTM, use high effort speech tasks to increase motor output across the speech mechanism. While LSVT LOUD® and the SpeechViveTM share the same therapeutic target (increased speech intensity), they differ substantially in the type of cueing used in therapy. LSVT LOUD® targets louder speech using internal, self-initiated cues. The SpeechViveTM, in contrast, elicits louder speech using a naturalistic, external noise cue. While data show that LSVT LOUD® and the SpeechViveTM both yield significant improvements in sound pressure level (SPL)/vocal intensity, the supportive physiologic adjustments used by speakers are not well understood. Our long-term goal is to improve voice rehabilitation for persons with PD. Our objectives are to determine the influence of treatment on the respiratory and laryngeal adjustments used by speakers with PD to support increased speech volume, and to identify the perceptions of physical and mental effort associated with each form of therapy. Our central hypothesis is that treatment strategy will differentially impact the physiologic systems that support louder speech and mediate speaker perceptions of effort. We plan to objectively test our central hypothesis and, thereby, attain the objective of this application by pursuing the following two specific aims:

**Aim 1:** To examine physiologic adjustments in respiratory and laryngeal function in response to treatment utilizing internal cueing (LSVT LOUD®) and external cueing (SpeechViveTM) strategies. Based on published research and preliminary data, we hypothesize that the external cueing treatment will elicit more efficient respiratory and laryngeal patterns during louder speech, in comparison to the internal cueing treatment.

**Aim 2:** To assess participants' level of perceived physical and mental effort associated with LSVT LOUD® and SpeechViveTM therapies. We hypothesize that speakers with PD will assign lower ratings of perceived physical and mental effort for SpeechViveTM therapy, in comparison to LSVT LOUD®. This hypothesis is predicated on programmatic differences in training intensity level and cognitive load.

## Methods

**Participants:** Thirty-six individuals with a neurological diagnosis of idiopathic PD will be enrolled for study in West Lafayette, Indiana (and surrounding areas) and in Amherst, Massachusetts (and surrounding areas). Participants will be randomly assigned to one of three groups: LSVT LOUD® (n=12), SpeechViveTM (n=12), non-treatment PD control (n=12). Participants assigned to the non-treatment control group will be sampled at the same time points as the experimental groups. The sample size has been chosen to detect a 5 dB SPL difference with a study power of 0.8 and significance level of 0.05. Inclusionary criteria include: (i) problems with speech volume as determined by an ASHA-certified speech-language pathologist, (ii) unaided hearing in at least one ear (to accommodate the SpeechViveTM), (iii) non-smoking in the past 5 years, (iv) no recent history of respiratory illness; (v) no neurological conditions other than PD and no history of neurosurgeries, (vi) free of depressive symptoms (Beck Depression Inventory score < 19), (vii) no voice therapy or voice therapy maintenance within the last six months, (viii) negative laryngeal pathology as determined by a videolaryngoscopic examination. Participants who present with normal vocal fold closure or incomplete vocal fold closure will be included for study. Patients with vocal fold lesions, hyperadduction, or other laryngeal pathology will be excluded and referred for treatment.

**Methods and Analysis:** LSVT LOUD® and SpeechViveTM follow a standardized treatment protocol which will ensure treatment fidelity across sites. The research personnel responsible for administering treatment will be LSVT LOUD®-certified and trained in the SpeechViveTM protocol. Data will be collected at three time points for each group: pre-treatment, mid-treatment, and immediately post-treatment. In accordance with specific aim 1, outcomes measures will include sound pressure level (SPL), utterance length, respiratory kinematic patterns, and laryngeal aerodynamic patterns. Pre-to-post treatment changes in SPL will serve as a primary indicator on the effectiveness of each intervention technique. SPL and utterance length will be captured and analyzed during a two-minute monologue task. Respiratory and laryngeal aerodynamic data will be collected and analyzed during connect speech. Respiratory kinematic data will be captured using inductance plethysmography to transduce the movement of the ribcage and abdomen during a monologue and reading task. Laryngeal aerodynamic data will be captured during a sentence-level task (“Buy pop or pop a papa”) using a circumferentially-vented pneumotachograph mask. In accordance with specific aim 2, a modified version of the National Aeronautics and Space Administration Task Load Index (NASA-TLX) [46] will be used to examine the participants’ perceived level of physical and mental effort associated with LSVT LOUD® and SpeechViveTM therapies. Following each treatment session, participants will be instructed to complete the computerized NASA-TLX scale and assign a visual analogue rating for the Mental Demand (how much mental and perceptual activity was required) and Physical Demand (how much physical activity was required) domains. Higher scores reflect speakers’ perceptions of increased effort.

For specific aim 1, the statistical approach will involve a repeated measures analysis of variance for each outcome variable: SPL, utterance length, respiratory kinematic measures, and laryngeal aerodynamic measures. The within-subject factor will be Session (pre, mid, post) and the between-subject factor will be Group (LSVT LOUD®, SpeechViveTM, and non-treatment control). Participant will be included as a random effect in the model to account for expected inter-subject differences in response to treatment. If the measures exhibit strong skewness or outlying values, we will compare the groups using appropriate non-parametric methods. Bonferroni-adjusted p-values will be used to reduce Type I error. For specific aim 2, each domain score of the NASA-TLX will be statistically analyzed using a separate, repeated measures analysis of variance. Treatment session will be included as a factor in each analysis. The model will include random effects to account for within-subject correlation. If the measures exhibit strong skewness or outlying values, we will compare the groups using non-parametric methods. Bonferroni-adjusted p-values will be used to reduce Type I error.

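### SPL is compared between arms as raw pre-to-post change; adjusting for pre-treatment SPL would be more precise unless the pre-post correlation is high, and costs almost nothing

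*Combined protocol and SAP*

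**What the plan says.** In Methods, under Methods and Analysis, the plan says: "Pre-to-post treatment changes in SPL will serve as a primary indicator on the effectiveness of each intervention technique".

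The Aim 1 statistical paragraph that follows applies a repeated-measures ANOVA to SPL and to each other Aim 1 measure: "The within-subject factor will be Session (pre, mid, post) and the between-subject factor will be Group". It adds: "Participant will be included as a random effect in the model to account for expected inter-subject differences in response to treatment". Multiplicity is handled by one sentence, "Bonferroni-adjusted p-values will be used to reduce Type I error", without the number of tests.

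In the Participants paragraph, 36 people are randomised in three groups of 12. Controls are measured too: "Participants assigned to the non-treatment control group will be sampled at the same time points as the experimental groups". On size, it says: "The sample size has been chosen to detect a 5 dB SPL difference with a study power of 0.8 and significance level of 0.05".

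No section names pre-treatment SPL as a covariate or sets the pre-treatment means equal across arms. The plan does not name the Group by Session interaction either, but a model with free pre-treatment means in each arm is the ordinary reading of this ANOVA.

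**The concern.** Randomisation makes the expected pre-treatment means equal, so an observed difference between arms at baseline is chance. A contrast of raw changes subtracts that chance difference in full. An adjusted contrast subtracts only the part that predicts the later value.

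The participant random effect does not do this. With complete data and a free pre-treatment mean in each arm, the participant intercept cancels from post minus pre. The fitted pre-to-post contrast is then the raw difference in mean change, whatever the size of the random-effect variance.

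What is at stake is precision. With 12 per arm and Bonferroni adjustment, the planned contrast may give a wider interval and less power for 5 dB than the same data could give.

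**Working it through.** **The plan's own figure.** Twelve per group cannot be reproduced, because no SD is stated. Solving for the SD that gives "study power of 0.8 and significance level of 0.05" for 5 dB with 12 per arm (two-sided, two groups) yields about 4.18 dB (t, 22 df), 4.24 (33 df) or 4.37 (normal approximation). I use 4.17 dB as an assumption.

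**Other assumptions.** The pre-post correlation (rho) is not stated, so a range is shown. Data are complete. Variances and correlations are equal across sessions (compound symmetry), which is what a random intercept implies.

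**Formulas** (s = SD, n = 12 per arm, 36 − 3 = 33 between-participant df):
- Planned contrast: variance = 2s²(1 − rho)(2/n), on 66 df.
- Single-time ANCOVA: variance = s²(1 − rho²)(2/n)(32/31), on 32 df. The factor 32/31 = 1 + 1/(33 − 2) is the cost of estimating the slope. Ratio to planned = (1 + rho)/2 × 32/31.
- Mid-and-post model with pre as covariate: the post difference is the adjusted mid-post average plus half the post-minus-mid difference. Per participant, these have variances s²(1 − rho)(1 + 2rho)/2 and s²(1 − rho)/2. Ratio to planned = ((1 + 2rho) × 32/31 + 1)/4.

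**Example, rho 0.5.** Planned variance = 2 × 17.39 × 0.5 × 2/12 = 2.898, SE 1.702, half-width 1.997 × 1.702 = 3.40 dB. Adjusted ratio = (2 × 1.0323 + 1)/4 = 0.766, variance 2.220, SE 1.490, half-width on about 57 df = 2.002 × 1.490 = 2.98 dB.

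| rho | Variance ratio, mid-and-post | Variance ratio, ANCOVA | 95% half-width (dB), planned / mid-and-post / ANCOVA | df, mid-and-post |
|---|---|---|---|---|
| 0.3 | 0.66 | 0.67 | 4.02 / 3.28 / 3.36 | 61 |
| 0.5 | 0.77 | 0.77 | 3.40 / 2.98 / 3.05 | 57 |
| 0.7 | 0.87 | 0.88 | 2.63 / 2.46 / 2.52 | 54 |
| 0.8 | 0.92 | 0.93 | 2.15 / 2.07 / 2.11 | 53 |
| 0.9 | 0.97 | 0.98 | 1.52 / 1.51 / 1.54 | 52 |

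To match the mid-and-post width, the planned contrast would need about 17.8, 15.4, 13.6 and 12.9 per arm at rho 0.3, 0.5, 0.7 and 0.8.

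**Power for 5 dB** (noncentral t), planned v mid-and-post, at rho 0.3, 0.5, 0.7 and 0.8:
- Bonferroni over two contrasts (each therapy v control): 0.58 v 0.77, 0.74 v 0.85, 0.93 v 0.96, 0.99 v 0.99.
- Over three: 0.51 v 0.72, 0.68 v 0.81, 0.91 v 0.94, 0.98 v 0.99.
- Over three, if 4.17 is instead the SD of change: 0.68 throughout v 0.87, 0.81, 0.75, 0.72.

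**Break-even on interval width** against the 66-df contrast: rho 0.93 for mid-and-post and 0.86 for single-time ANCOVA. Were change tested on its own 33-df error, the ANCOVA figure would be 0.93. The equal-baseline model, simulated, had variance ratios of about 0.66, 0.76, 0.86, 0.90 and 0.96 at the tabled rho values, and still 0.997 at rho 0.99, so it showed no break-even on variance.

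**Simulation under compound symmetry** (20,000 trials per setting): coverage was 0.949 to 0.952 and null rejection 0.016 to 0.018 at alpha 0.0167 for all models.

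**Departures from compound symmetry.**
- Response SD of 3 dB in the therapy arms, half that at mid (assumed): simulated mid-and-post ratios were 0.82, 0.92, 0.96 and 1.00 at underlying rho 0.5, 0.7, 0.8 and 0.9.
- Post SD 1.1 times pre SD: single-time ANCOVA ratios are 0.73, 0.84, 0.95, 1.00 and 1.03 at rho 0.3, 0.5, 0.7, 0.8 and 0.9. At 1.25 times they are 0.92 at rho 0.5 and 1.01 at rho 0.7.
- Limit on the loss: with k = post SD / pre SD, the same in each arm, the ANCOVA ratio is (32/31) × k²(1 − rho²)/(1 + k² − 2k rho). Denominator minus numerator of the second factor is (1 − k rho)², never negative, so the ratio cannot exceed 32/31 = 1.03. For mid-and-post under compound symmetry, the variance ratio as rho nears 1 is (3 × 32/31 + 1)/4 = 1.02, and the interval is at most about 2% wider.

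**The case against.** The strongest reply is that a Group by Session ANOVA is conventional and unbiased under randomisation, and that the size of the gain rests on two figures the documents do not give. That stands. At rho 0.7 to 0.8 the gain is small, and nothing in the documents shows that rho is as low as 0.3 to 0.5.

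A second reply concerns compound symmetry. The plan itself expects participants to respond differently, which would raise post-treatment variance in the therapy arms. This also stands: it shrinks the gain and lowers the break-even. It does not favour the planned contrast, though. In the 3 dB response simulation, coverage was 0.938 to 0.946 for mid-and-post and 0.922 to 0.942 for the planned contrast with pooled error.

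Third, the sentence on SPL change speaks of each technique, so it can be read as change within each arm. The gain does not apply to that quantity. A reader might infer that within-arm change must be demoted; neither the documents nor the precision argument requires it.

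Two other stronger readings are tempting. One is that the planned analysis is biased or invalid; it is not. The other is that a single threshold of 0.93 governs every form of adjustment. It belongs to the mid-and-post model under compound symmetry; single-time ANCOVA and the equal-baseline model behave differently.

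Finally, nothing was calculated for utterance length or for the respiratory and laryngeal measures. The ratios depend only on rho under the stated assumptions, but rho for those measures is equally unknown.

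**Conclusion.** The point holds as one of efficiency. The planned between-arm SPL contrast is valid but gives up precision unless rho is high. Under compound symmetry with 12 per arm and complete data, adjustment removes about 34%, 23%, 13%, 8% and 3% of the variance at rho 0.3, 0.5, 0.7, 0.8 and 0.9. With variable response or modestly larger post-treatment variance, the saving is smaller and break-even falls to roughly 0.8 to 0.9. The variance ratios do not depend on the SD; the half-widths and power figures rest on the back-solved 4.17 dB. The algebra is secure. How much this trial would gain cannot be settled from the documents, so they do not support a claim that the trial is underpowered because of this choice. The trade is still favourable: a possibly material gain against a loss of about 2 to 3%.

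**What to change.** In the Aim 1 statistical paragraph, state that between-arm differences in post-treatment SPL (each therapy v control) will be estimated from a repeated-measures model with mid and post values as outcomes; Group, Session and Group by Session as factors; pre-treatment SPL as covariate; and the participant random effect, with Satterthwaite or Kenward-Roger df. Alternatively, keep pre as an outcome and constrain its mean to be equal across arms.

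Use the same form for the other Aim 1 measures, including LSVT LOUD v SpeechVive for the hypothesis that "the external cueing treatment will elicit more efficient respiratory and laryngeal patterns during louder speech, in comparison to the internal cueing treatment". Apply the plan's Bonferroni rule to these contrasts and state how many there are. Report within-arm pre-to-post changes as planned. Settle the model before outcomes are seen.

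Cost: plan wording, a fall in error df from 66 to about 52 to 61 (already counted in the widths and power above), and a slightly wider interval if rho is very high. No new data, visits or participants are needed.

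### The plan ties effectiveness to each therapy's own pre-to-post SPL change and commits to no between-group contrast of change, so the randomised control is not tied to the conclusion

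*Combined protocol and SAP*

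**What the plan says.** All locations are in the combined protocol and SAP.

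- **Methods, Methods and Analysis paragraph.** The only effectiveness criterion is "Pre-to-post treatment changes in SPL will serve as a primary indicator on the effectiveness of each intervention technique". It is worded per technique and does not mention the control arm.
- **Methods, Participants paragraph.** Allocation is random to three arms: "LSVT LOUD® (n=12), SpeechViveTM (n=12), non-treatment PD control (n=12"). The control is measured concurrently: "Participants assigned to the non-treatment control group will be sampled at the same time points as the experimental groups". The size is justified by "The sample size has been chosen to detect a 5 dB SPL difference", with "study power of 0.8" and "significance level of 0.05". The text does not say whether the 5 dB is a difference in post-treatment values, a difference in change, or a change within an arm.
- **Methods, closing statistical paragraph.** For each Aim 1 outcome, "The within-subject factor will be Session (pre, mid, post) and the between-subject factor will be Group", with the two therapies and the control as levels of Group and participant as a random effect. No interaction, contrast, baseline covariate or decisive test is named. The non-parametric fallback compares groups but does not say on what quantity. Bonferroni adjustment is promised without a number of comparisons.
- **Background, Aim 1.** The hypothesis compares the two therapies on the efficiency of respiratory and laryngeal patterns. It is not a hypothesis about SPL.

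**The concern.** The design includes a randomised, concurrently measured untreated arm, which is what separates a therapy effect from a change that would have happened anyway. The effectiveness sentence does not use it. Two sources of such change are plausible. SPL is measured on a repeated monologue task, so familiarity may raise it. Entry requires a problem with speech volume, so some regression to the mean is possible.

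The named model does not close the gap:

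- The Session effect pools treated and untreated arms.
- The Group effect averages in the pre-treatment session, where no therapy effect can exist.
- The interaction has (3-1) x (3-1) = 4 degrees of freedom and, taken alone, does not say which arms differ or at which session.

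Some follow-up is therefore needed, and the effectiveness sentence leaves room for it to be a pre-to-post test within each arm. That would risk crediting a non-specific gain to therapy. It would also invite reading significance in one therapy arm but not the other as a difference between therapies, which it is not.

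**Working it through.** **1. The plan's own figure.** The 12 per arm cannot be reproduced, because no SD, sidedness, test or estimand is given. Solving backwards for the SD at which 12 per arm gives 80% power for 5 dB (two-sided 0.05, noncentral t, 22 df) gives 4.18 dB. A paired test within one arm reaches 80% power at an SD of change of 5.63 dB. The stated size therefore fits a between-group or a within-arm target, depending on the unstated SD.

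**2. Inputs.**
- From the documents: 12 per arm, alpha 0.05, 5 dB.
- Assumed: SD 4.18 dB at each session (from step 1), pre-post correlation r from 0.3 to 0.8, equal correlation between all sessions, no dropout, and a shift of 1 or 2 dB common to all arms. The documents give no figure for the shift.

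**3. Chance that an inert therapy is significant within its arm.** SD of change = 4.18 x sqrt(2(1-r)). The paired t test has 11 df and noncentrality shift / (SD of change / sqrt(12)). At r = 0.5 and 2 dB, for example: SD of change = 4.18 x sqrt(1) = 4.18, noncentrality = 2 / (4.18/3.464) = 1.66, probability 0.33.

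| r | SD of change (dB) | 1 dB shift | 2 dB shift | 2 dB shift, tested at 0.05/3 |
|---|---|---|---|---|
| 0.3 | 4.95 | 0.10 | 0.25 | 0.12 |
| 0.5 | 4.18 | 0.12 | 0.33 | 0.17 |
| 0.7 | 3.24 | 0.17 | 0.50 | 0.30 |
| 0.8 | 2.64 | 0.22 | 0.67 | 0.46 |

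A shift common to all arms cancels in a between-group comparison of change, so that test stays at 0.05 throughout.

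**4. Discordant verdicts on equal therapies.** If both therapies truly gain 3 dB, each within-arm test is significant with probability p = 0.48 / 0.62 / 0.83 / 0.95 at r = 0.3 / 0.5 / 0.7 / 0.8. The chance that exactly one is significant is 2p(1-p), or about 0.50 / 0.47 / 0.28 / 0.10.

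**5. Does power favour one test?** Both therapies gain 5 dB at post, control gains 0, r = 0.5, alpha 0.05 unadjusted.

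| Effect present at mid-treatment | Group main effect (2 df) | Interaction F(4, 66) | Three-group test of pre-to-post change (2 df) |
|---|---|---|---|
| Half | 0.41 | 0.75 | 0.83 |
| Full | 0.65 | 0.87 | 0.83 |

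The interaction and the change test swap places with the mid-treatment assumption, which the documents do not give. At r = 0.3 with the full effect at mid, even the Group main effect (0.76) exceeds the change test (0.685). These tests also address different hypotheses.

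**6. Power of the proposed contrasts.** For one 5 dB contrast at r = 0.5, unadjusted, on 22 df: change score (SD 4.18) 0.80; baseline-adjusted (SD = 4.18 x sqrt(1-0.25) = 3.62) 0.90. With three contrasts adjusted as one family (0.05/3) and error pooled over all three arms (33 and 32 df): about 0.66 and 0.80.

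**The case against.** The strongest reply is that the plan already does the right thing by convention. The control is randomised and is a level of Group in the SPL model. A mixed analysis with Session and Group normally includes their interaction, which is the between-group test of change. The fallback compares groups. No paired within-arm test appears anywhere, and the effectiveness sentence can be read as naming only an outcome and an interval.

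Much of this stands, and it rules out three stronger readings:

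- *The plan specifies within-arm tests.* It does not. The wording permits them, and the figures in steps 3 and 4 apply only if they are used.
- *The model cannot test a between-group difference in change.* It can. What is missing is a commitment to that comparison.
- *The chosen test loses power.* No decisive test is named, and step 5 shows that the ranking depends on unstated quantities. If the proposed contrasts are adjusted as a family of three, their power on change scores (about 0.66) is below the 0.75 or 0.87 of the unadjusted interaction.

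The shift is also an assumption: the documents contain no evidence of a retest gain in monologue SPL, and at 1 dB the risk is modest.

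The reply does not supply a decisive comparison. Even with the interaction fitted, the 4-df result answers neither the therapy-versus-control nor the therapy-versus-therapy question, and the only sentence that says how effectiveness is judged leaves the control out.

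**Conclusion.** The concern holds as a failure to commit to a comparison. The effectiveness criterion is not tied to the randomised control, and no between-group contrast of change is named for SPL or for the measures that Aim 1's hypothesis concerns.

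If within-arm tests were used to fill the gap, false credit to an inert therapy would be about 10-22% with a 1 dB common shift and 25-67% with a 2 dB shift, against 5% for a between-group test of change. These figures rest on the back-solved SD, a correlation of 0.3 to 0.8 and the assumed shift. That the contrast is missing can be read directly from the text and rests on none of them. The correction should be made, but it does not call the design into question.

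**What to change.** In the Methods and Analysis paragraph, state that each therapy's effectiveness is its difference from control in pre-to-post SPL change.

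In the statistical paragraph, state that:

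- the Aim 1 hypothesis is tested by the SpeechVive minus LSVT LOUD difference in pre-to-post change on the respiratory and laryngeal measures, with the same contrast reported for SPL. An SPL contrast alone would not test that hypothesis;
- each comparison is a 1-df Group by Session contrast with a 95% confidence interval, preferably adjusted for the pre-treatment value. Under randomisation the adjusted comparison estimates the same difference, and with more power on the assumptions above;
- within-arm changes are descriptive;
- the non-parametric fallback compares the same quantity, pre-to-post change;
- the Bonferroni adjustment covers a named set of contrasts.

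The Participants paragraph should say which contrast the 5 dB refers to and give the SD behind it.

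The cost is a few sentences, with no new data, visits or participants. The downside is multiplicity. Adjusting three contrasts as one family lowers power for 5 dB at correlation 0.5 to about 0.66 on change scores or 0.80 with baseline adjustment, so the family should be chosen deliberately and stated in advance.

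### Aim 1 uses plain Bonferroni; Holm holds the same 0.05 family-wise error, never rejects less, and costs only a change of text

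*Combined protocol and SAP*

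**What the plan says.** All references are to the Combined protocol and SAP, Methods.

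- **Design.** "Participants will be randomly assigned to one of three groups", with 12 in each of LSVT LOUD, SpeechVive and non-treatment control.
- **Sample size.** "The sample size has been chosen to detect a 5 dB SPL difference with a study power of 0.8 and significance level of 0.05". No SD, contrast or sidedness is given, and the multiplicity adjustment is not mentioned.
- **Main measure.** "Pre-to-post treatment changes in SPL will serve as a primary indicator on the effectiveness of each intervention technique".
- **Model for Aim 1.** A repeated measures ANOVA for each outcome: "The within-subject factor will be Session (pre, mid, post) and the between-subject factor will be Group". Participant is a random effect, and non-parametric methods are the fallback for skewed or outlying data.
- **Multiplicity.** "Bonferroni-adjusted p-values will be used to reduce Type I error". The plan does not say whether the family is the group pairs, the sessions, the outcomes or some combination. The same sentence appears again for Aim 2.

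**The concern.** Plain Bonferroni tests every member of a family of m hypotheses at 0.05/m, whatever the other results are. Holm controls the same error rate under the same conditions but relaxes the threshold after each rejection. With 36 participants fixed, the procedure is one of the few choices left that can add power without adding people. It bears on the treatment-versus-control contrasts and also on the treatment-versus-treatment comparison in Aim 1, where external cueing is expected to give "more efficient respiratory and laryngeal patterns during louder speech, in comparison to the internal cueing treatment". Any replacement must name its family, because the number of tests sets the thresholds.

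**Working it through.** **1. The plan's own figure.** From Methods, Participants: difference 5 dB, n = 12 per group, power 0.8, level 0.05. Assumed because not stated: two-sided test, no dropout, and a one-way comparison of pre-to-post change with pooled variance on 36 - 3 = 33 df. Without an SD the 0.8 cannot be reproduced, only back-solved:

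- Non-centrality = 5 / (SD x sqrt(2/12)).
- Power = P(|T| > critical value), T non-central t on 33 df. At 0.05 the critical value is 2.035.
- Power is 0.80 at SD = 4.24 dB, where the non-centrality is 5 / (4.24 x 0.408) = 2.89.

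This SD is an illustration, not a design input.

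**2. Bonferroni.** For three group pairs the level is 0.05/3 = 0.0167, the critical value is 2.522 and power is 0.64. With 2, 6 or 9 tests it is 0.70, 0.54 or 0.48.

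**3. Holm.** Order the p-values. With three tests, compare the smallest with 0.05/3, the next with 0.05/2 and the last with 0.05, stopping at the first failure. No threshold is below 0.05/3, so every Bonferroni rejection is kept. The first step is the same as Bonferroni's, so the chance of at least one rejection is the same. This ordering needs no SD.

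**4. Overall test, then pairs.** Test the 2-df Group effect at 0.05 and, only if it is significant, each pair at 0.05. With exactly three groups this is a closed test: if all groups are equal, the gate holds 0.05; if just one pair is equal, there is only one true null and it is tested at 0.05. The argument covers three group pairs on one outcome and one session contrast, and nothing wider.

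**5. Size of the gain.** Simulated trials (at least 400,000 per setting), 12 per group, 33 df, SD 4.24, three pairs; power for a 5 dB contrast:

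| Mean changes (treatment, treatment, control) | Bonferroni | Holm | Overall test, then pairs |
|---|---|---|---|
| 5, 5, 0 | 0.644 | 0.678 | 0.752 |
| 5, 4, 0 | 0.644 | 0.663 | 0.716 |
| 5, 2.5, 0 | 0.644 | 0.652 | 0.685 |
| 5, 0, 0 | 0.644 | 0.678 | 0.751 |

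Holm adds 0.008 to 0.034. With means 5, 5, 0:

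- At least one treatment-versus-control contrast significant: 0.79 (Bonferroni), 0.79 (Holm), 0.82 (overall test, then pairs).
- Both significant: 0.50, 0.57, 0.68.

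For scale, Bonferroni reaches 0.688 with 13 per group, 0.729 with 14 and 0.765 with 15. Holm's best value here is therefore worth less than one participant per group.

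**6. Error control.** Probability of any false rejection (same order of methods): 0.043, 0.043, 0.050 with all groups equal; 0.017, 0.050, 0.050 with one group far from the other two.

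**7. Other readings of the 0.8** (Bonferroni / Holm / overall test, then pairs):

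- 0.05 already family-wise over three pairs (SD 3.62): 0.80 / 0.81-0.83 / 0.83-0.88.
- 0.05 is the level of an overall ANOVA: 0.62 / 0.65 / 0.73 (means 5, 5, 0; SD 4.35) or 0.76 / 0.77 / 0.80 (means 5, 2.5, 0; SD 3.77).
- SD varied, means 5, 5, 0: 0.83 / 0.86 / 0.90 at SD 3.5; 0.48 / 0.51 / 0.59 at SD 5.0.
- Session x Group model, 66 df, equal correlation between sessions: 0.65 / 0.66-0.68 / 0.69-0.75.
- Family of two treatment-versus-control contrasts (SD 4.24): Bonferroni 0.70; Holm 0.71-0.76 if both treatments have an effect and 0.705 if the other has none.
- 5 dB as a within-group change (n = 12, 11 df): Bonferroni 0.68 for two tests and 0.61 for three. Holm cannot be lower, but the size of any gain was not calculated.

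**The case against.** The best case for leaving the text alone is that it contains no error. Bonferroni is valid for any family, carries over to the non-parametric fallback and gives simultaneous confidence intervals directly. Holm's gain is a few points at most in the three-pair settings with control lowest, close to nothing for two control contrasts when one treatment is inert, and nil for the chance of at least one finding. Every power figure rests on an SD that the plan does not give. All of this stands, and it limits the point to a cheap improvement. It does not remove it, because Holm's advantage follows from its thresholds and not from the SD, and the plan gives no reason, such as a wish for simultaneous intervals, for preferring Bonferroni.

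A second objection concerns the overall-test route. It fits only if the family is the three group pairs on one outcome and one session contrast. If the Bonferroni sentence was meant to span sessions or outcomes, testing each outcome this way would not hold the same error rate. Gating every outcome on pre-to-post change would also drop the mid-treatment session from inference, and no non-parametric version of the gate is specified. It also missed a pair that Bonferroni rejected in 0.2-0.4% of simulated trials; Holm never did. These points stand, so the route is offered only as a conditional option.

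A third concerns intervals. Unadjusted 95% intervals can exclude zero for a pair that the test does not reject: about 9-13% of simulated trials under the overall-test route when groups differ. That is a real cost and must be handled in the text.

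**Conclusion.** The point holds as an efficiency improvement. Plain Bonferroni is valid but dominated by Holm at the same 0.05 family-wise error. For three group pairs at 12 per group and an assumed SD of 4.24 dB, power for a 5 dB contrast goes from 0.64 to 0.65-0.68, with no change in the chance of at least one significant contrast. If the family is exactly the three pairs in pre-to-post SPL change, the overall test followed by pairs gives 0.68-0.75.

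Three stronger readings are not supported:

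- **That the stated 0.8 is wrong, or that true power is 0.64.** The plan does not say whether "study power of 0.8 and significance level of 0.05" refers to a per-comparison, family-wise or overall test. If 0.05 is family-wise, nothing is lost.
- **That Type I error is uncontrolled.** Bonferroni controls it within whatever family is named.
- **That a known gain applies to the Aim 1 hypothesis on respiratory and laryngeal patterns.** The plan gives no effect size for those measures, so only Holm's ordering carries over, not the figures.

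**What to change.** 1. In the statistical paragraph of Methods, Aim 1, replace the Bonferroni sentence with: *P-values within [the stated family] will be adjusted by the Holm procedure at a family-wise level of 0.05.* The sponsor names the family. This works for any family and with the non-parametric fallback.
2. Optional, only if the family is defined as the three group pairs in pre-to-post SPL change: *The overall Group effect on pre-to-post SPL change (2 df) is tested at 0.05; only if it is significant is each pairwise difference tested at 0.05, two-sided.* Keep the Session x Group ANOVA with the mid session as planned, and do not use this gate for families that span sessions or outcomes.
3. Report either Bonferroni simultaneous intervals, noting that these can include zero for a contrast that the chosen test rejects, or unadjusted 95% intervals labelled as descriptive.
4. As a clarification, when the sample size sentence is next edited, say whether its 0.05 is before or after adjustment. The back-solved SDs used here should not be written in as design inputs.

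The cost is text only, with no extra participants. What is given up is the direct match between Bonferroni tests and their simultaneous intervals.
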